### 9.3. Clinical Laboratory Tests

#### 9.3.1. Laboratory Value Definitions

Laboratory values and change from baseline values will be summarized descriptively by visit. Baseline will be determined according to Section 4.1.3. If there are multiple values that meet the criteria for baseline, additional rules may be provided after consultation with the medical monitor to delineate which value will be defined as baseline.

Laboratory values and change from baseline values will be summarized descriptively by visit. The baseline value will be determined using the nonmissing values collected before the first dose, prioritizing scheduled assessments for baseline identification over unscheduled visits. The last record before administration in the highest priority will be considered the baseline record. For baseline laboratory candidates with the same date and time in the same priority category, additional rules may be provided after consultation with the medical monitor to delineate which value will be defined as baseline.

Laboratory test values will be assessed for severity based on the numerical component of CTCAE v5.

#### 9.3.2. Laboratory Value Summaries

Any laboratory test results and associated normal ranges from local laboratories will be converted to SI units. Scheduled laboratory tests for hematology and clinical chemistry will be summarized by scheduled study days (eg, Days 3, 5, 7) through Day 29. Windows for postbaseline by-visit summaries will be  $\pm 1$  study day (eg, Day 3 will be Days 2-4).

When there are multiple nonmissing laboratory values for a participant's particular test within a visit window, the convention described in Table 5 will be used to determine the record used for by-visit tabulations and summaries. A record may only be used for 1 scheduled visit. If a record qualifies for more than 1 by-visit summary, then the earlier study day will take precedence.

**Table 5: Identification of Records for Postbaseline By-Visit Summaries**

Priority	Laboratory Visit	Proximity to Visit Window	Tiebreaker
1	Scheduled	In-window	Use smallest laboratory sequence number
2	Unscheduled	In-window	
3	Scheduled	Out-of-window	

Numeric laboratory values will be summarized descriptively in SI units, and non-numeric test values will be tabulated when necessary. In addition, line graphs and box-and-whisker plots will

be provided for hemoglobin, platelet counts, leukocytes, lymphocytes, neutrophils, creatinine, ALT, and AST.

Severity grades will be assigned to laboratory test values based on the numerical component of CTCAE v5. Shift tables will be presented showing change in CTCAE grade from baseline to worst grade postbaseline. Separate summaries for abnormally high and abnormally low laboratory values will be provided when the laboratory parameter has both high and low grading criteria. The denominator for the percentage calculation will be the number of participants in the baseline category. Shift tables will also be presented showing change in CTCAE grade from baseline to the last value using the same methods explained above. The number of participants who experienced worsening of laboratory abnormalities will be summarized by maximum severity.

### 9.3.3. Potential Drug-Induced Liver Injury Events

Participants with potential drug-induced liver injuries will be listed. Potential drug-induced liver injuries will be defined in participants with normal ALT and AST and total bilirubin at baseline as having elevated ALT or AST  $> 3 \times$  ULN accompanied by total bilirubin  $> 2 \times$  ULN at the same visit. Potential drug-induced liver injuries will be defined in participants with elevated ALT or AST or total bilirubin at baseline as having elevated ALT or AST  $> 2 \times$  baseline or ALT or AST  $> 300$  U/L, whichever occurs first, accompanied by total bilirubin  $> 2 \times$  baseline and total bilirubin  $> 2 \times$  ULN at the same visit.

## 9.4. Vital Signs

Values at each scheduled visit, change, and percentage change from baseline for vital signs, including systolic blood pressure, diastolic blood pressure, pulse, temperature, respiratory rate, pulse oximetry, and body weight will be summarized descriptively. Normal ranges for vital signs are provided in [Table 6](#).

**Table 6: Normal Ranges for Vital Sign Values**

Parameter	12 – < 16 years a		≥ 16 years	
	High	Low	High	Low
Systolic blood pressure (mmHg)	≤ 131.0	≥ 90.0	≤ 155.0	≥ 85.0
Diastolic blood pressure (mmHg)	≤ 83.0	≥ 64.0	≤ 100.0	≥ 40.0
Pulse (beats per minute)	≤ 100.0	≥ 60.0	≤ 100.0	≥ 45.0
Body temperature (°C)	≤ 38.0	≥ 35.5	≤ 38.0	≥ 35.5
Respiratory rate (breaths per minute)	≤ 20.0	≥ 12.0	≤ 24.0	≥ 8.0

a [Novak and Gill 2020](#).

## 10. INTERIM ANALYSES

Per SAP Amendment 3, no interim analysis will be performed.

## 11. CHANGES AND MODIFICATIONS TO THE ANALYSIS PLAN

All versions of the SAP are listed in [Table 7](#).

**Table 7: Statistical Analysis Plan Versions**

SAP Version	Date
Original	21 APR 2020
Amendment 1	11 AUG 2020
Amendment 2	22 SEP 2020
Amendment 3	22 FEB 2020

### 11.1. Changes to Protocol-Defined Analyses

#### 11.1.1. Original to Amendment 1

- The analysis for time to improvement from baseline category to earliest 1-point improvement in the ordinal scale was restated as time to improvement from baseline category to earliest improvement of any kind.
- After FDA feedback, the initial plan for treatment groups continued beyond rejection of their specific null hypothesis at the efficacy interim analysis where final reported p-values would be based on the highest level of significance achieved, either at the interim or final analysis, was modified to report p-values from the final analysis at final reporting.
- Gender was removed from analyses of the primary and secondary endpoints and added as a sensitivity analysis for the primary endpoint.

#### 11.1.2. Amendment 1 to Amendment 2

- The weekly overall survival futility analysis was replaced by a conditional power analysis to occur after approximately every 50 participants enrolled have at least 2 weeks of follow-up.
- The reference level of ARDS severity was changed to be mild/moderate instead of severe.

#### 11.1.3. Amendment 2 to Amendment 3

- Section 3.2, Section 3.3, Section 5.1, Section 7.3.1, Section 7.3.3, Section 10, Appendix A – The interim analysis and conditional power analysis were removed. The only remaining analysis will be the final analysis.
- Section 3.2, Section 5.3.3, Section 5.3.5, Section 7.2, Section 7.5.1, Section 7.5.2, Section 7.5.3, Appendix A – The alpha control strategy for the primary efficacy analysis was changed. The definition of the PP population was modified, and the PD-evaluable population was removed. Any planned analyses that previously used the PD-evaluable population will use the safety population instead.

## 11.2. Changes to the Statistical Analysis Plan

### 11.2.1. Original to Amendment 1

The following changes to the SAP were made based upon FDA comments on the original Protocol and SAP:

- Figure 1 – Updated to account for the changes in inclusion criteria.
- Section 7.3.1 – An estimator for the treatment group proportions and their difference was added.
- Section 7.3.2 – The age subgroup analyses were modified to < 18 years, 18-64 years, or ≥ 65 years.
- Section 7.3.3 – A tipping point analysis was added for the primary endpoint, and a comparison of the 2 placebo images (5 mg BID and 15 mg BID) was added.
- Section 7.4.2.1 – The proposed test for the proportional odds assumption was removed, and a sensitivity analysis was added to the comparison of the COVID-19 9-point ordinal scale.
- Section 7.4.3 – Additional details were added regarding the summary of SOFA components.
- Section 9.4 – Table 7 was added to define normal ranges for vital signs based on age categories.

The following editorial changes were also made based upon findings and additional feedback:

- Section 7.3.2 – Additional subgroup analyses were added for prior or concomitant remdesivir, prior or concomitant convalescent plasma, concomitant anticoagulant use, concomitant corticosteroid use, and prior biologic use.
- Section 7.4.3.1 – Editorial changes were made to the LDA model description, with minor modifications to the SAS code provided.
- Section 9.2.2 – AE summaries inconsistent with the planned tables and summaries were removed.
- Section 9.3.3 – Updated the definition of potential drug-induced liver injuries to be consistent with the Protocol.
- Section 10.3.1 – The formula for Dunnett's procedure was corrected to reflect that the joint probability should be subtracted from each marginal probability.

Other minor administrative changes have been incorporated throughout and are noted in the redline version of the document.

### **11.2.2. Amendment 1 to Amendment 2**

The following changes to the SAP were made based upon findings and additional feedback:

- Section 4.1.4 and Section 9.2.1 – A typo was corrected for the AE follow-up period to align with the Protocol.
- Section 6.1.2 – Variables were modified and added to what will be summarized for baseline disease characteristics.
- Section 6.2 – The number and percentage of randomized participants were removed from the disposition section since this is not part of the standard disposition table, the count can be obtained from the analysis populations table for the ITT population.
- Section 7.3.3, Section 10.1, Section 10.2, and Section 10.4.2 – A Cox regression model was replaced with conditional power analysis.
- Section 7.4.3.1 – Minor modifications were made to the SAS code.

Other minor administrative changes have been incorporated throughout and are noted in the redline version of the document.

### **11.2.3. Amendment 2 to Amendment 3**

The following changes to the SAP were made based upon findings and additional feedback:

- Section 7.4.3.1, Appendix A – The analysis of the endpoint for Change from baseline to Day 3, 5, 8, 11, 15, and 29 in SOFA score was changed from an LDA model to a simple descriptive summary.
- Section 9.5 – The electrocardiogram section was removed since that data was not collected.
- Section 6.1.3 – Summary of Prior Medications for COVID-19 was removed.

## APPENDIX A. PLANNED TABLES, FIGURES, AND LISTINGS

This appendix provides a list of the planned tables, figures, and listings for the Clinical Study Report. Shells are provided in a separate document for tables that are not in the Standard Safety Tables v1.7.

The lists of tables, figures, and listings are to be used as guidelines. Modifications of the lists that do not otherwise affect the nature of the analysis will not warrant an amendment to the SAP.

### Tables

Table No.	Title	Population	Standard
Baseline and Demographic Characteristics			
1.1 Disposition			
1.1.1	Analysis Populations	ITT	X
1.1.2	Summary of Participant Disposition	ITT	X
1.1.3	Summary of Number of Participants Enrolled by Country and Site	ITT	X
1.1.4	Summary of Protocol Deviations	ITT	X
1.2 Demography and Baseline Characteristics			
1.2.1	Summary of Demographics and Baseline Characteristics	ITT	X
1.3 Baseline Disease Characteristics			
1.3.1	Summary of Baseline Disease Characteristics and History	ITT	
1.4 Prior Medication and Concomitant Medication			
1.4.1	Summary of Prior Medications	ITT	X
1.4.2	Summary of Concomitant Medications	ITT	X
1.5+ Others			
1.5.1	Summary of General Medical History	ITT	X
Efficacy			
2.1 Primary Efficacy			
2.1.1	Summary of 28-Day Mortality Analyzed by Logistic Regression Model	ITT	
2.1.2	Summary of 28-Day Mortality Analyzed by Logistic Regression Model	PP	
2.1.3	Summary of 28-Day Mortality Analyzed by Logistic Regression Model Using Actual PaO 2 /FiO 2 at Randomization	ITT	
2.1.4	Summary of 28-Day Mortality Analyzed by Logistic Regression Model Treating Participants who are Lost to Follow-Up on or Before Day 29 as Deaths	ITT	
2.1.6	Summary of Tipping Point Analysis for 28-Day Mortality	ITT	
2.1.7	Summary of 28-Day Mortality for Participants Assigned Placebo by Treatment Image	ITT	
2.2 Secondary Efficacy			
2.2.1	Summary of Day 29 In-Hospital Outcomes by Treatment Group	ITT	
2.2.2.1	Summary of COVID-19 Ordinal Scale at Day 1, Day 15, and Day 29	ITT	
2.2.2.2.1	Summary of COVID-19 Proportional Odds Model at Day 15 and Day 29	ITT	

Table No.	Title	Population	Standard
2.2.2.2.2	Summary of COVID-19 Proportional Odds Model at Day 15 and Day 29	PP	
2.2.2.3.1	Summary of Participants With a 2-Point Improvement in COVID-19 Ordinal Scale on Day 15 or Day 29	ITT	
2.2.2.3.2	Summary of Participants With a 1-Point Improvement in COVID-19 Ordinal Scale on Day 15 or Day 29	ITT	
2.2.3.4	Kaplan-Meier Analysis of Time From Randomization to First Improvement in COVID-19 Ordinal Scale	ITT	
2.2.4	Summary of Change in COVID-19 Ordinal Scale at Study Day 15 and 29	ITT	
2.2.5	Summary of COVID-19 Ordinal Scale by Study Day	ITT	
2.2.6.1	Summary of Change in SOFA Score at Days 3, 5, 8, 11, 15, 29	ITT	
2.2.6.2	Summary of SOFA Score at Study Days 1, 3, 5, 8, 11, 15, and 29	ITT	
2.2.6.3	Summary of SOFA Score Components at Study Days 1, 3, 5, 8, 11, 15, and 29	ITT	
2.3 Exploratory Endpoint			
2.3.1	Summary of Participants Receiving IL-6, IL-6R, IL-1RA, IL-1 beta, GM-CSF, BTK, or JAK Directed Therapies by Day 15 and by Day 29	Safety	
2.3.2	Summary of Serum Markers of Inflammation at Baseline, Day 15, and Day 29 by Treatment Group	Safety	
2.3.3.1	Summary of SARS-CoV2 Virology at Baseline, Day 15, and Day 29	Safety	
2.3.3.2	Summary of SARS-CoV2 Antibody Testing at Baseline, Day 15, and Day 29	Safety	
Safety			
3.1 Dose Exposure			
3.1.1	Summary of Exposure and Duration of Exposure to Ruxolitinib/Placebo	Safety	X
3.1.2	Summary of Average Daily Dose by Study Day	Safety	X
3.1.3	Summary of Study Medication Compliance	Safety	X
3.2 Adverse Events			
3.2.1	Overall Summary of Treatment-Emergent Adverse Events	Safety	X
3.2.2	Summary of Treatment-Emergent Adverse Events by MedDRA System Organ Class and Preferred Term	Safety	X
3.2.3	Summary of Treatment-Emergent Adverse Events by MedDRA Preferred Term in Decreasing Order of Frequency	Safety	X
3.2.4	Summary of Treatment-Emergent Adverse Events by MedDRA System Organ Class, Preferred Term, and Maximum Severity Category	Safety	X
3.2.6	Summary of Grade 3 or Higher Treatment-Emergent Adverse Events by MedDRA System Organ Class and Preferred Term	Safety	X
3.2.7	Summary of Grade 3 or Higher Treatment-Emergent Adverse Events by MedDRA Preferred Term in Decreasing Order of Frequency	Safety	X
3.2.8	Summary of Serious Treatment-Emergent Adverse Events by MedDRA System Organ Class and Preferred Term	Safety	X

Table No.	Title	Population	Standard
3.2.9	Summary of Serious Treatment-Emergent Adverse Events by MedDRA Preferred Term in Decreasing Order of Frequency	Safety	X
3.2.10	Summary of Ruxolitinib/Placebo Treatment-Related Treatment-Emergent Adverse Events by MedDRA System Organ Class and Preferred Term	Safety	X
3.2.11	Summary of Ruxolitinib/Placebo Treatment-Related Treatment-Emergent Adverse Events by MedDRA Preferred Term in Decreasing Order of Frequency	Safety	X
3.2.13	Summary of Ruxolitinib/Placebo Treatment-Related Treatment-Emergent Adverse Events by MedDRA System Organ Class, Preferred Term, and Maximum Severity Category	Safety	X
3.2.14	Summary of Grade 3 or Higher Ruxolitinib/Placebo Treatment-Related Treatment-Emergent Adverse Events by MedDRA System Organ Class and Preferred Term	Safety	X
3.2.15	Summary of Ruxolitinib/Placebo Treatment-Related Serious Treatment-Emergent Adverse Events by MedDRA System Organ Class and Preferred Term	Safety	X
3.2.16	Summary of Treatment-Emergent Adverse Events With a Fatal Outcome by MedDRA System Organ Class and Preferred Term	Safety	X
3.2.18	Summary of Treatment-Emergent Adverse Events Leading to Ruxolitinib/Placebo Dose Reduction by MedDRA System Organ Class and Preferred Term	Safety	X
3.2.19	Summary of Treatment-Emergent Adverse Events Leading to Ruxolitinib/Placebo Dose Interruption by MedDRA System Organ Class and Preferred Term	Safety	X
3.2.20	Summary of Treatment-Emergent Adverse Events Leading to Discontinuation of Ruxolitinib/Placebo by MedDRA System Organ Class and Preferred Term	Safety	X
3.2.21	Summary of Treatment-Emergent Adverse Events Requiring Concomitant Medications by MedDRA System Organ Class and Preferred Term	Safety	X
3.3 Laboratory			
3.3.1.1	Summary of Laboratory Values - Hematology	Safety	X
3.3.1.2	Summary of Laboratory Values - Chemistry	Safety	X
3.3.3.1	Shift Summary of Hematology Laboratory Values in CTC Grade - to the Worst Abnormal Value	Safety	X
3.3.3.2	Shift Summary of Chemistry Laboratory Values in CTC Grade - to the Worst Abnormal Value	Safety	X
3.3.3.3	Treatment-Emergent Worsening of Laboratory Abnormalities - Hematology	Safety	X
3.3.3.4	Treatment-Emergent Worsening of Laboratory Abnormalities - Chemistry	Safety	X
3.3.5.1	Shift Summary of Hematology Laboratory Values in CTC Grade - to the Last Value	Safety	X
3.3.5.2	Shift Summary of Chemistry Laboratory Values in CTC Grade - to the Last Value	Safety	X
3.4 Vital Signs			
3.4.1	Summary of Systolic Blood Pressure	Safety	X
3.4.2	Summary of Diastolic Blood Pressure	Safety	X

Table No.	Title	Population	Standard
3.4.3	Summary of Pulse	Safety	X
3.4.4	Summary of Respiration Rate	Safety	X
3.4.6	Summary of Weight	Safety	X
3.4.7	Summary of Pulse Oximetry	Safety	
3.4.8	Summary of Mean Arterial Pressure	Safety	

## Figures

Figure No.	Title
4.1 Primary Efficacy	
4.1.2	Forest Plot of Odds Ratio and 95% CIs for 28-Day Mortality Rate
4.2 Secondary Efficacy	
4.2.1	Kaplan-Meier Estimates of Time From Randomization to First Improvement in COVID-19 Ordinal Scale
4.2.2	Stacked Bar Chart of COVID-19 Ordinal Scale by Treatment Group
4.3 Exploratory Efficacy	
4.3.1	Box-and-Whisker Plot of Ferritin by Study Visit
4.3.2	Box-and-Whisker Plot of CRP by Study Visit
4.3.3	Box-and-Whisker Plot of D-Dimer by Study Visit
4.3.4	Box-and-Whisker Plot of Procalcitonin by Study Visit
4.3.5	Box-and-Whisker Plot of IL-6 by Study Visit
4.6 Laboratory Data	
4.6.1	Box-and-Whisker Plot of Selected Laboratory Values by Study Visit

## Listings

Listing No.	Title
2.1.1	Participant Disposition Status
2.1.2	Participant Enrollment and Site Information
2.2.1	Protocol Deviations
2.2.2	Randomized Participants With Inclusion/Exclusion Criteria Violations
2.3	Analysis Population
2.4.1	Demographic and Baseline Characteristics
2.4.2	Medical History
2.4.3	COVID-19 Baseline Disease Characteristics
2.4.4	Prior Medications for COVID-19
2.4.5	Prior and Concomitant Medications
2.4.6	PBRC/Platelet Transfusions
2.4.7	Procedures and Non-Drug Therapies
2.5.1	Ruxolitinib/Placebo Exposure and Compliance
2.6.1	Deaths and 28-Day Mortality
2.6.2	COVID-19 Ordinal Scale by Study Day
2.6.4	COVID-19 Improvement Events and Assessment
2.6.5	Hospitalization, Ventilation, and Intubation Status
2.6.6	SOFA Scores and Components by Study Day

Listing No.	Title
2.6.7	Arterial Blood Gas Analyses
2.6.8	Deaths
2.6.9	Chest Imaging
2.6.10	Concomitant IL-6, IL-6R, IL-1RA, IL-1 beta, GM-CSF, BTK, or JAK Directed Therapies
2.6.11	Serum Markers of Inflammation
2.6.12	SARS-CoV2 Virology
2.6.13	SARS-CoV2 Serology
2.7.1	Adverse Events
2.7.2	Serious Adverse Events
2.7.3	Grade 3 and Higher Adverse Events
2.7.4	Fatal Adverse Events
2.7.5	Ruxolitinib/Placebo Treatment-Related Adverse Events
2.7.6	Serious Ruxolitinib/Placebo Treatment-Related Adverse Events
2.7.7	Adverse Events Leading to Ruxolitinib/Placebo Dose Interruption
2.7.8	Adverse Events Leading to Ruxolitinib/Placebo Dose Reduction
2.7.9	Adverse Events Leading to Discontinuation of Ruxolitinib/Placebo
2.8.1.1	Abnormal Clinical Laboratory Values - Hematology
2.8.1.2	Clinical Laboratory Values - Hematology
2.8.1.3	Abnormal Clinical Laboratory Values - Chemistry
2.8.1.4	Clinical Laboratory Values - Chemistry
2.8.1.5	Potential Drug Induced Liver Injuries
2.8.2.1	Abnormal Vital Sign Values
2.8.2.2	Vital Sign Values

## APPENDIX B. COVID-19 9-POINT ORDINAL SCALE

Participant State	Descriptor	Score
Uninfected	No clinical or virological evidence of infection	0
Ambulatory a	No limitation of activities	1
	Limitation of activities	2
Hospitalized Mild Disease	Hospitalized, no oxygen therapy (defined as SpO 2 ≥ 94% on room air)	3
	Oxygen by mask or nasal prongs	4
Hospitalized Severe Disease	Noninvasive ventilation or high-flow oxygen	5
	Intubation and mechanical ventilation	6
	Ventilation + additional organ support – vasopressors, RRT, ECMO	7
Dead	Death	8

a Defined as not in hospital or in hospital and ready for discharge.

Source: [WHO 2020](#).

## APPENDIX C. SEQUENTIAL ORGAN FAILURE ASSESSMENT

The SOFA score is a scoring system to determine the extent of a person's organ function or rate of failure (Vincent et al 1996, Vincent et al 1998). The score is based on six different scores, one each for the respiratory, cardiovascular, hepatic, coagulation, renal, and neurological systems. Baseline assessment should be based on data collected closest to (but also prior to) randomization. Each subsequent day should use the worst value for each parameter in the preceding 24-hour period.

### Respiratory System

When using PaO2:

PaO2/FiO2 (mmHg)

- 0 = PaO2/FiO2 ≥ 400
- 1 = PaO2/FiO2 < 400
- 2 = PaO2/FiO2 < 300
- 3 = PaO2/FiO2 < 200 and mechanically ventilated
- 4 = PaO2/FiO2 < 100 and mechanically ventilated

PaO2 should be used if available. However, if PaO2 is not available, the following table can be used to generate the SOFA score with SpO2 (Pandharipande et al 2009):

### Use of SpO2/FiO2 in SOFA Score

SOFA Respiratory System Points (Using SpO 2 )	SpO 2 /FiO 2 Ratio		
	PEEP < 8 or Not Intubated	PEEP 8-12	PEEP > 12
0	≥ 457	≥ 515	≥ 425
1	< 457	< 515	< 425
2	< 370	< 387	< 332
3	< 240	< 259	< 234
4	< 115	< 130	< 129

Note: The original SpO2/FiO2 Ratio as published would require a SpO2 > 110% to achieve a SOFA score of 0. Therefore, this score has been modified to accept a SpO2 of 96% or greater on room air as normal (ie, an SpO2/FiO2 ratio of ≥ 457 would be a SOFA score = 0).

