- ^g Vital signs will be collected once daily while hospitalized between 7:00 AM and 12:00 PM local time and include heart rate, respiratory rate, systolic and diastolic blood pressure, and body temperature. Not required after discharge.
- ^h Arterial blood gases will be collected during screening, within 6 hours of planned randomization, to assess PaO₂/FiO₂. Thereafter, ABGs will be performed daily while 1) the participant is receiving mechanical ventilation, OR 2) the participant has an arterial line. Parameters including pH, PaO₂, PaCO₂, and SaO₂ will be collected for each ABG. SpO₂ (pulse oximetry) will be recorded in the eCRF once daily while hospitalized. ABGs and SpO₂ not required after discharge.
- ¹ Ventilator settings (as applicable) will be collected once daily between 7:00 AM and 12:00 PM local time. Settings to be collected include mode, FiO₂, PEEP, VT, and respiratory rate. Dates of intubation and extubation (if applicable) will be recorded. Supplemental oxygen support post-extubation will be collected daily through Day 29, until hospital discharge.
- ^j If participant is discharged, a telephone call may be used to perform assessment. See Appendix B for scale.
- ^k Beginning at Day 15, the participant may continue treatment up to Day 28 at the discretion of the investigator and after approval by the sponsor medical monitor.
- ¹ Hematology, clinical chemistry, and markers of inflammation should be measured by the local laboratory. See Section 9.4.3 for required analytes. If participant is discharged, local laboratory assessments may be performed on Day 15 and/or Day 29 if feasible.
- ^m An optional serum sample will be collected at Day 1 (predose) and Day 7 and 15 for cytokine analysis. See Section 9.5.1 for collection, processing, storage and shipment instructions.
- ⁿ Pregnancy test: only for females of childbearing potential, serum pregnancy test (serum hCG) will be performed at screening assessment. Serum or urine test is acceptable at subsequent assessment(s).
- ° Screening chest imaging may be ≤ 2 days prior to Day 1.

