- P All medications, procedures, and significant non-drug therapies administered from randomization through Day 29 must be recorded on the appropriate eCRF. Additionally, antivirals and therapeutic agents administered for SaRS-CoV-2 infection/COVID-19 infection and treatments for COVID-19 pneumonia/ARDS administered within 14 days of randomization must also be recorded. If participant is discharged from the hospital, the scheduled assessments may be performed via telephone.
- ^q The SOFA score is to be determined per Appendix C. Not required after discharge from the ICU. SpO₂ method for calculating respiratory score may be used if arterial blood gases were not performed on corresponding assessment day.
- ^r In-hospital outcomes will be collected on eCRFs as outlined in Section 9.3.5.

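### The SpO2-based SOFA table lets non-intubated participants with a ratio below 240 score 3 or 4, although the PaO2 rule reserves those scores for ventilated participants

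*SAP*

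**What the plan says.** SAP Appendix C (Respiratory System), repeated in Protocol Appendix C, scores the respiratory component from PaO2/FiO2 when PaO2 is available. Three points need a ratio "< 200 and mechanically ventilated" and four need a ratio "< 100 and mechanically ventilated". Lower scores carry no ventilation condition.

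If PaO2 is not available, a table based on SpO2/FiO2 may be used. Its first column is headed "PEEP < 8 or Not Intubated", with cutoffs of 457, 370, 240 and 115 for the steps from 0 to 4. Rows 3 and 4 do not mention ventilation. A note explains that the published cutoff for a zero score required an impossible saturation, so the score was changed to accept an SpO2 of "96% or greater on room air as normal". The PEEP 8-12 column still shows 515 for a zero score.

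Footnotes to Protocol Table 3 settle which method applies on a given day. After screening, "ABGs will be performed daily while 1) the participant is receiving mechanical ventilation, OR 2) the participant has an arterial line". The SpO2 "method for calculating respiratory score may be used if arterial blood gases were not performed on corresponding assessment day". Protocol Section 9.3.4 has the sites calculate SOFA, use the worst value of the preceding 24 hours, and stop at ICU discharge.

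SOFA change at Days 3, 5, 8, 11, 15 and 29 is a secondary endpoint, summarized descriptively (SAP Section 7.4.3.1). Component scores are compared by a Cochran-Mantel-Haenszel test described as exploratory (SAP Section 7.4.3.2).

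**The concern.** The two methods are meant to be interchangeable, but they disagree for participants off the ventilator, and neither document says which prevails. Which method applies also depends on a post-randomization event. Everyone enters intubated with a screening blood gas, so baseline normally follows the PaO2 rule. After extubation without an arterial line no blood gas is scheduled, and the SpO2 table is the method the plan offers. The scoring rule can therefore change at the moment the participant improves, and in the direction that withholds the fall in score that the PaO2 rule would record.

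If treatment affects extubation, the effect would not fall evenly across arms. SAP Section 7.4.3.1 also fills a missing intermediate day with the worse of its two neighbouring scores, so a high value can carry to an adjacent gap.

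**Working it through.** **Inputs.** PaO2 rule and SpO2 table: Appendix C of either document. Method rules: Protocol Table 3 footnotes. Assumption: room air is FiO2 0.21; the documents say room air without a figure. The ratio is SpO2 in percent divided by FiO2 as a fraction.

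**1. Reproduce the plan's own figure.** 96 / 0.21 = 457.1, which matches the 457 in the note and in the first column.

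**2. Maximum without ventilation.** Under the PaO2 rule, 3 and 4 both require ventilation, so the maximum is 2. Under the SpO2 table's non-intubated column, the maximum is 4.

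**3. Where the two conflict.** The table gives 3 when SpO2 / FiO2 < 240, that is when FiO2 > SpO2 / 240. It gives 4 when FiO2 > SpO2 / 115.

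| SpO2 | FiO2 above which score is at least 3 | FiO2 above which score is 4 |
|---|---|---|
| 90% | 90/240 = 0.375 | 90/115 = 0.783 |
| 94% | 94/240 = 0.392 | 94/115 = 0.817 |
| 100% | 100/240 = 0.417 | 100/115 = 0.870 |

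**4. Examples for a participant off the ventilator with no blood gas that day.**

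| SpO2, FiO2 | Ratio | Table score | PaO2 rule maximum | Excess |
|---|---|---|---|---|
| 94%, 0.36 | 261 | 2 | 2 | 0 |
| 94%, 0.40 | 235 | 3 | 2 | 1 |
| 95%, 0.50 | 190 | 3 | 2 | 1 |
| 95%, 0.85 | 112 | 4 | 2 | 2 |

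The excess is 0 at ratios of 240 or more, 1 point from 115 to below 240, and 2 points below 115.

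**5. What this does to change scores.** Take a participant who scored 3 while ventilated (PaO2/FiO2 below 200) and is then extubated, with SpO2 95% on FiO2 0.50. The table gives 3, a change of 0. With the PaO2 rule's maximum applied, the score is at most 2, a fall of at least 1. If the ventilated score was 4 and the later ratio is 112, the table again shows no change, where the maximum would give a fall of at least 2.

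**6. The 515 cell.** 515 x 0.21 = 108.2% saturation. The highest possible ratio on room air is 100 / 0.21 = 476, so the lowest attainable score in the PEEP 8-12 column is 1. The other zero cutoffs are reachable: 457 x 0.21 = 96.0% and 425 x 0.21 = 89.3%.

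**The case against.** The strongest reply is that few records are affected and that the right score is not established. A record must come from a participant who is off the ventilator, still in the ICU, without a blood gas that day, with a ratio below 240, and on an analysis day. The documents give no frequency for arterial lines or blood gases after extubation, so no count can be offered. Because SOFA takes the worst value of the preceding 24 hours, a blood gas drawn before extubation may still govern on that day. Not intubated is also not the same as not ventilated. The ordinal scale lists non-invasive ventilation separately, and Appendix C does not say whether it counts as mechanical ventilation; if it does, 3 or 4 is permitted for those participants under both rules. All of this stands and limits the size of the point. It does not remove the conflict for participants on high-flow or mask oxygen.

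A reader might infer more than the documents support:

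- **That the 515 cutoff inflates scores after extubation.** It sits in the PEEP 8-12 column. The non-intubated column uses 457, which is reachable at 96% on room air. The 515 cell costs at most 1 point, for someone at PEEP 8-12 at or near room air and without a blood gas, although ventilated participants have daily gases.
- **That improvement is reversed.** A rise at extubation would require a ventilated PaO2 score of 2 or less followed by an SpO2/FiO2 ratio below 240. The documents do not say how the two ratios correspond, so such a rise cannot be separated from a real loss of oxygenation. What is shown is a fall that goes unrecorded.
- **That all extubated participants score too high.** Ratios of 240 or more are unaffected, and too high means only relative to the PaO2 rule.

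**Conclusion.** Appendix C is inconsistent as written. Followed literally, it scores some non-ventilated ICU participants 1 or 2 points above the PaO2 rule's maximum of 2, out of a total SOFA maximum of 6 x 4 = 24. This can mask improvement at extubation in a secondary endpoint that is only described and in an exploratory component test. The mortality primary does not use SOFA and is unaffected.

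The size per record rests on FiO2 0.21 for room air (for the zero cutoffs only) and on taking the PaO2 rule's ventilation condition as the reference. The number of affected records cannot be estimated from the documents. The unreachable 515 is a separate error with negligible effect. The point is minor, but cheap to settle.

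**What to change.** Add to the SAP derivation, before unblinding:

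1. On days without mechanical ventilation, cap the respiratory component at 2 and reduce the total SOFA score by the same amount. This needs only ventilation status and the intubation and extubation dates, which the trial collects. It leaves scores derived correctly from PaO2 unchanged.
2. State whether non-invasive ventilation counts as mechanical ventilation, and how the day of extubation is treated, given the 24-hour look-back.
3. Keep the site-recorded score as a sensitivity summary.
4. Reconcile the 515 cell with the table's note.

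The cost is one derivation step that departs from some site-entered scores. Rewording the appendix alone would not change scores that sites have already entered; enrollment stopped at 211 participants.

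A full central re-derivation from SpO2/FiO2 is not proposed. FiO2 is listed with ventilator settings and blood gases but not with oxygen support after extubation, and SpO2 is recorded once daily rather than as a 24-hour worst value.
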